#### 4.2.1 Data safety monitoring board

A data safety monitoring board (DSMB) is installed to review the trial's progress including data quality and safety data. No interim review regarding efficacy will be performed and therefore the efficacy data can remain blinded throughout the course of the study. Safety data, consisting of serious adverse events, adverse events and suspected unexpected serious adverse events are reported directly from the researchers to the DSMB and will be unblinded. Recruitment data (e.g. data return rates, treatment compliance) will be provided to the DSMB by the research team. The DSMB will meet at least once a year. An extra meeting may be scheduled on request of the principal investigators, study coordinator or of the members of the DSMB.

#### 4.3 End points

##### *Primary end point:*

- Number of postnatal transfusions per infant from birth up to 3 months of life.

##### *Secondary end points:*

[figure not shown]
- Number of postnatal transfusions per infant  $\geq 7$  days up to 3 months of life.
- The percentage of infants requiring a postnatal transfusion up to 3 months of life;
- Time from birth to first postnatal transfusion (days);
- Hemoglobin level at first postnatal transfusion (g/dl);
- Number of days of hospitalization and readmission(s) associated with erythrocyte transfusion(s);
- Course of hemoglobin up to 3 months of life.

*Safety end points:*

- The percentage of infants with a systolic blood pressure  $\geq 2$  SD above age adjusted mean systolic blood pressure during treatment;
- The percentage of infants with ferritin levels  $>200$   $\mu\text{g/L}$  during treatment.

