# 5.2 Study design

Randomized controlled trial. Included neonates will be randomized at birth to treatment with EPO (intervention group) or "standard of care", 1:1 allocation. In the treatment group, EPO (darbepoetin alfa) is administered subcutaneously at a dosage of 10 µg/kg once a week, starting at day 7, for a period of 8 weeks. Treatment is administered during weekly home visits after discharge from the LUMC. Concomitant therapy with folate (0.25 mg/day) is given

in both groups (standard practice). Concomitant iron therapy is given if ferritin level drops below 75 microg/l. Weekly routine measurements of complete blood counts (including hemoglobin level, hematocrit and reticulocyte count) will be performed in both groups (standard practice). EPO is discontinued if hemoglobin level is  $\geq$  13 g/dL after at least 4 weeks of treatment with EPO. Blood pressure will be measured at the start of treatment, after four weeks and after eight weeks. Monthly measurements of liver enzymes (aspartate aminotransferase (ASAT), alanine aminotransferase (ALAT), gamma-glutamyl transferase ( $\gamma$ GT) and lactate dehydrogenase (LDH)) will also be performed in all groups (standard practice). In addition, the neonatal EPO-level will be determined at the start of the treatment with EPO. The number of top-up transfusions received during the first 3 months of life and hemoglobin levels prior to the top-up transfusion are recorded. After initial discharge from the LUMC, top-up transfusions are performed when hemoglobin levels fall below 7.2 g/dL or when hemoglobin is between 7.2 and 8.8 g/dL if clinical symptoms of anemia (lethargy, feeding difficulties or failure to thrive) are present.

At two years of age a physical and neurological examination and an assessment of cognitive and neurological development using the Dutch version of the Bayley Scales of Infant Development, third edition (BSID-III) will be performed (standard practice). BSID-III scores provide mental developmental indexes (MDI) and psychomotor development indexes (PDI).

[figure not shown]

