#### 5.10 Statistical analysis

Both intention to treat and per protocol analysis will be carried out to study the differences in outcome measures between the intervention and control group. Intention to treat analysis is our primary choice of analysis. A minimal treatment with 5 out of 8 darbepoetin injections is defined as acceptable protocol deviation. A p-value < 0.05 will be considered to indicate statistical significance. The number of top-up transfusions per infant and, the number of days of admission for top-up transfusions will be compared between both groups using a Mann-Whitney U test. The time from birth to top-up transfusion will be compared between both groups using survival analysis and a log rank test. The percentage of infants requiring a top-up transfusion up to 2 months of life, the percentage of infants with a high blood pressure and the percentage of infants with high ferritin levels will be compared between both groups using  $\chi^2$  tests. If despite randomization the groups differ at baseline in type of alloimmunization, EPO-levels at birth or treatment with exchange transfusion, a multivariable model may be used in a secondary analysis to correct for these factors.

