#### 6.2 Neonatal baseline characteristics

The following variables will be recorded: birth weight, gestational age at birth, gender, Apgar score at 5 min, respiratory distress syndrome, patent ductus arteriosus, necrotizing enterocolitis, sepsis and cerebral lesions on cranial ultrasound examination, number of days of phototherapy, number of exchange transfusions, and highest bilirubin level during admission. At birth, the following measurements will be performed in umbilical cord blood as part of standard care: hemoglobin level, hematocrit, reticulocyte count, nucleated red cells (erythroblasts), iron tests (including serum iron, total iron binding capacity, transferrin and ferritin), liver enzymes (ASAT, ALAT, γGT and LDH). Additionally, EPO-levels will be measured in umbilical cord blood.

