#### 6.3 Measurements during follow-up

Complete blood counts including hemoglobin level and reticulocyte count are determined weekly in both groups (standard practice). The number of top-up transfusions received during the first 3 months of life and hemoglobin levels prior to the top-up transfusion are recorded. Iron tests (serum iron, ferritin, transferrin and total iron binding capacity) and liver enzymes (ASAT, ALAT, YGT and LDH) will be determined monthly (standard practice). Blood pressure will be measured at the start of treatment, after four weeks and after eight weeks of treatment.

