4.4 Sample size calculation

Based on the (scarce) results in the literature, we expect a 50% reduction in the median number of total postnatal transfusions per patient with EPO treatment, from a median of 2 to 1. For sample size calculation we hypothesized a shift in the distribution of number of transfusions per infant as depicted in Figure 1. The distribution in the 'care as usual' group are based on data from 2000-2014. Based on these expected frequencies, group sample sizes of 21 achieve 81% power to detect a difference of 1.1 between the null hypothesis that both group means are 1.9 and the alternative hypothesis that the mean of the EPO group is 0.8 with estimated group standard deviations of 1.5 and 0.9 and with a significance level (alpha) of 0.05 using a two-sided Mann-Whitney test. The drop-out percentage is estimated at 5%, adding  $(42/0.95 = 44)$  1 infant to each group's sample size.

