### 5.2 Analysis of primary and secondary outcomes

The total number of postnatal transfusions per infant from birth to the end of the follow-up period, the number of postnatal transfusions per infant  $\geq 7$  days (which is at the start of intervention in the treatment group) and the number of days of additional admissions for postnatal erythrocyte transfusions will be compared between both groups using a Mann-Whitney U test. The time from birth to first postnatal transfusion will be compared between both groups using a log rank test and will be displayed using Kaplan-Meier survival curves (in this case transfusion-free survival) by treatment group. The period of follow-up in this study is 90 days and as such the end point for included infants that do not receive transfusions during this period, is 90 days in the survival analysis. The percentage of infants requiring a postnatal transfusion up to 3 months of life will be compared between both groups using a  $\chi^2$  test. The average or median number, depending on shape of distribution, of EPO injections in the treatment arm will be reported, as well as a summary of reasons to discontinue EPO treatment.

A multiple linear regression analysis will be performed to correct the association between treatment assignment and the primary outcome (number of postnatal transfusions). The following potential

confounders identified from previous research [unpublished data] are to be corrected for if, despite randomization, there is a baseline difference between the groups: type of alloimmunization, EPO-levels at birth, number of IUTs and treatment with exchange transfusion. In case of a non-normal distribution of the number of postnatal transfusions per neonate, log transformation will be applied. If the assumptions underlying linear regression are violated, or if the value zero occurs often, a Poisson regression will be fitted. If the number of postnatal transfusions per infant <7 days of life shows a difference between the two groups, a sensitivity analysis will be performed by performing the multiple linear regression analysis (or Poisson regression) with and without the transfusions administered <7 days. This will differentiate between the clinical course of early and late anemia and will evaluate more specifically the effect of EPO treatment, which is started at 7 days of age.

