## 5.1 Figures and tables

**Figure 1. Flowchart of study participants**

**Figure 2. Kaplan Meier survival curves for time to first postnatal transfusion by treatment group**

**Figure 3. Hemoglobin course over time by treatment group**

**Table 1. Baseline demographic and clinical characteristics by treatment group**

	EPO treatment (n=22)	Standard care (n=22)
Male - n (%)		
Cesarean delivery - n (%)		
Gestational age at birth - weeks		
Number of IUTs per neonate		
Gestational age at first IUT - weeks		
Hemoglobin level at first IUT - g/dl		
Birth weight - gram		
Hemoglobin level at birth - g/dl		
Reticulocyte count at birth - ‰		
Endogenous erythropoietin at birth - U/L		
Apgar score at 5 minutes		
RhD alloimmunization - n (%)		
Rhc alloimmunization - n (%)		
Kell alloimmunization - n (%)		
Phototherapy - days		
Treatment with exchange transfusions - n (%)		
Maximum bilirubin - mg/dl		

a Value given as mean  $\pm$  SD

b Value given as median (IQR)

**Table 2. Postnatal transfusions and safety measures in EPO treated infants and infants treated according to standard care**

	EPO treatment (n=22)	Standard care (n=22)	p-value
Total number of RBC transfusions per neonate			
Number of RBC transfusions per neonate $\geq 7$ days			
Treatment with postnatal RBC transfusion - n (%)			
Number of days before first transfusion			c
Hemoglobin level at first transfusion - g/dl		-	
Initial hospitalization - days			
Additional hospitalization - days			
Infants with systolic blood pressure $\geq 2$ SD above age adjusted mean during treatment - n (%)		-	
Infants with ferritin levels $>200$ $\mu\text{g/L}$ during treatment - n (%)		-	

a Value given as mean  $\pm$  SD

b Value given as median (IQR)

c Log rank test

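### The ferritin safety endpoint is an absolute on-treatment threshold and no analysis uses the cord-blood ferritin already collected, so a persisting high value cannot be told from a new one

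*SAP*

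**What the plan says.** **Endpoint.** Protocol 5.5 (as a secondary endpoint) and SAP 4.3 (as a safety endpoint) use the same definition: "The percentage of infants with ferritin levels" above 200 µg/L during treatment. Neither adds a baseline condition, a new-onset rule or a change criterion.

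**Ferritin data.** Protocol 6.2 has "iron tests (including serum iron, total iron binding capacity, transferrin and ferritin") done in cord blood at birth as standard care. Protocol 6.3 repeats them monthly: "Iron tests (serum iron, ferritin, transferrin and total iron binding capacity"). Dosing comes later, "starting at day 7, for a period of 8 weeks" (protocol 5.2).

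**Analysis.** Protocol 5.10 states that "the percentage of infants with high ferritin levels will be compared between both groups using" χ² tests, unadjusted. SAP 5.2 names no method for either safety endpoint. Its adjustment list is "type of alloimmunization, EPO-levels at birth, number of IUTs and treatment with exchange transfusion", which does not include ferritin, and that model is for the transfusion count only.

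**Tables.** SAP Table 1 has rows for hemoglobin and reticulocytes at birth and for "Endogenous erythropoietin at birth - U/L", but none for ferritin. SAP Table 2 shows a dash in both safety rows. From the table text it is not certain whether the dash belongs to the standard-care column or the p-value column.

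**Blood pressure.** SAP 4.2 has it measured in EPO-treated infants at onset of treatment and after four and eight weeks. The endpoint is a systolic value at least 2 SD above the age-adjusted mean during treatment. Neither document says whether the onset reading counts.

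**The concern.** Every infant enters after at least one intrauterine red cell transfusion, and the plan also anticipates exchange transfusion and transfusion in the first week. Ferritin that is already raised before the first dose is therefore plausible. An absolute threshold reached during treatment does not separate that earlier iron state from a change under the trial policy.

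The protocol treats iron as a safety matter: section 7.3 attributes earlier reports of retinopathy to excess iron. A reader of Table 2 will want to know whether high ferritin arose on treatment. The endpoint as written cannot answer that, although a value from before dosing is on file for the purpose. Blood pressure has a similar gap: an infant already at or above 2 SD at the onset reading could be counted as an on-treatment case.

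**Working it through.** **No figure to reproduce.** The documents give no expected ferritin rate, power or sample size for this endpoint. The only power statement, "group sample sizes of 21 achieve 81% power to detect a difference of 1.1", concerns the transfusion count and has no bearing here.

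**Timing.** The cord sample is taken on day 0. Dosing runs from about day 7 for 8 weeks, to about day 63 (7 + 56), so monthly sampling gives about two values in that window. Three histories all score as an event:

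1. high at birth and still high at a monthly sample;
2. not high at birth, raised by exchange or other transfusion on days 0–6, and still high at a monthly sample;
3. not high until dosing starts, then high.

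The cord value separates history 1 from the other two. It cannot separate 2 from 3, and no ferritin measurement at day 7 is specified.

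**Dilution (illustration; all rates assumed).** Let b be the share in each arm whose high level predates dosing and persists. Let new onset among the rest be 5% in standard care and 30% with EPO, with 22 infants per arm.

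- Visible rate = b + (1 − b) × new-onset rate.
- Visible difference = (1 − b) × 25 points.
- Share of EPO-arm events that predate dosing = b ÷ EPO rate.
- Power = Φ[(difference − 1.96 × SE₀) ÷ SE₁], with SE₀ pooled, SE₁ unpooled and two-sided alpha 0.05.

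For b = 40%:

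- Rates: 0.40 + 0.60 × 0.05 = 0.43 and 0.40 + 0.60 × 0.30 = 0.58. The difference is 0.15, and 0.40 ÷ 0.58 = 0.69.
- SE₀ = √(0.505 × 0.495 × 2/22) = 0.151.
- SE₁ = √[(0.43 × 0.57 + 0.58 × 0.42)/22] = 0.149.
- Power = 16.5%.

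| b | Standard care | EPO | Difference (points) | Power | EPO-arm events predating dosing | Infants per arm not already high, 22(1 − b) |
|---|---|---|---|---|---|---|
| 0% | 5% | 30% | 25 | 59.3% | 0% | 22 |
| 20% | 24% | 44% | 20 | 28.3% | 45% | 17.6 |
| 40% | 43% | 58% | 15 | 16.5% | 69% | 13.2 |
| 60% | 62% | 72% | 10 | 10.4% | 83% | 8.8 |
| 80% | 81% | 86% | 5 | 6.5% | 93% | 4.4 |

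The 59.3% in the first row is not what a new-onset analysis would recover at larger b, because fewer infants remain at risk.

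**Why not restrict to new onset.** Take b = 80% and 10% new onset in both arms. Then 4.4 infants per arm remain, with 4.4 × 0.10 = 0.44 expected events per arm. The SD of the between-arm difference is √(2 × 0.10 × 0.90/4.4) = 20 points. The crude rate would be 0.80 + 0.20 × 0.10 = 82%, with SD √(2 × 0.82 × 0.18/22) = 11.6 points. Restriction can therefore lose precision.

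**What adjustment gives.** Comparing log on-treatment ferritin with log cord ferritin as covariate keeps every infant who has both values. It multiplies the standard error by roughly √(1 − r²), where r is the within-arm correlation of the two. The documents give no value for r.

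**The case against.** **Allocation is randomized 1:1 and protocol 5.10 compares the arms.** High values from before dosing balance in expectation. A reader might infer that the comparison is biased, or that a high EPO percentage can never be informative. The documents support neither. This protection does require that the arms be compared; if the dash in Table 2 means that standard-care values are not shown, the cord value is the only reference left.

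**The cord value is not itself counted.** A reader might infer that any infant high at birth is automatically an on-treatment event. That is wrong: a monthly sample during treatment must still exceed 200 µg/L. Persistence is an assumption.

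**Chance imbalance is already allowed for.** It is tempting to argue that baseline imbalance swamps the new-onset rate. Take a prior share of 20%, 50% or 80%, with 10% of the rest newly crossing. New onset then contributes 0.10 × (1 − b) = 8, 5 or 2 points, while imbalance alone has SD √[2b(1 − b)/22] = 12.1, 15.1 or 12.1 points. The first figure is a level within one arm and the second is the SD of a difference between arms, so they cannot be ranked. Nor is the imbalance an extra error. At crude rates of 28%, 55% and 82%, the ordinary sampling SD of the difference is 13.5, 15.0 and 11.6 points, and a χ² test reckons with that.

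**An absolute threshold is a legitimate measure of iron load, whatever its origin.** This stands, and it is a reason to keep the crude endpoint. A new-onset subset would also drop infants in whom the arms might differ in how fast high ferritin resolves.

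**Cord blood is an imperfect baseline.** This also stands: it misses iron from transfusions on days 0–6.

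**Blood pressure is a different case.** With readings specified in the SAP only for EPO-treated infants, the argument about imbalance between arms does not apply to it.

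**Conclusion.** The point holds in a limited form. The endpoint ignores a value collected before dosing, in a population where raised ferritin before treatment is plausible. It therefore cannot show whether a high level persisted or arose on treatment, and an unadjusted comparison gives up precision at about 22 per arm. There is no systematic bias between arms.

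The size is unknown. Under the assumed new-onset rates of 5% and 30%, the visible difference falls from 25 points with no persisting share to 5 points at a share of 80%. If few infants are high at birth, or levels fall quickly, the loss is small. The conclusion rests on some persistence into a monthly sample and, for the gain in precision, on a correlation between cord and later ferritin.

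For blood pressure the issue is narrower: the onset reading should not be able to count as an on-treatment event. The primary analysis is not affected.

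**What to change.** Make these changes before the SAP is finalized and the database is locked:

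- **SAP 4.3:** keep the crude percentage above 200 µg/L as the stated endpoint. Say which sampling window corresponds to during treatment in the standard-care arm, which the documents leave undefined.
- **SAP Table 1:** add ferritin at birth.
- **SAP 5.2:** add a between-arm comparison of log on-treatment ferritin adjusted for log cord-blood ferritin, and state how an infant's monthly values are combined.
- **SAP Table 2:** show, by arm and descriptively, on-treatment status above 200 µg/L separately for infants with cord ferritin at or below 200 and above 200. Do not replace the endpoint with the new-onset subset.
- **Caveat in the text:** cord blood precedes dosing by about a week and does not capture exchange or top-up transfusions on days 0–6.
- **Blood pressure:** treat the onset reading as baseline. Count only the week-4 and week-8 readings as during treatment, and report how many of the infants counted were already at or above 2 SD at onset.

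The cost is some SAP wording and a few table rows. The protocol already provides for all these measurements. The downside is small cell counts in the descriptive split, which is why the crude percentage stays in place.

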4.4 Sample size calculation

Based on the (scarce) results in the literature, we expect a 50% reduction in the median number of total postnatal transfusions per patient with EPO treatment, from a median of 2 to 1. For sample size calculation we hypothesized a shift in the distribution of number of transfusions per infant as depicted in Figure 1. The distribution in the 'care as usual' group are based on data from 2000-2014. Based on these expected frequencies, group sample sizes of 21 achieve 81% power to detect a difference of 1.1 between the null hypothesis that both group means are 1.9 and the alternative hypothesis that the mean of the EPO group is 0.8 with estimated group standard deviations of 1.5 and 0.9 and with a significance level (alpha) of 0.05 using a two-sided Mann-Whitney test. The drop-out percentage is estimated at 5%, adding  $(42/0.95 = 44)$  1 infant to each group's sample size.

**Figure 1. Hypothesized distribution of number of postnatal transfusions**

## 5. Statistical analyses

### 5.1 Analysis sets

If after randomization parents or caregivers choose to withdraw the infant from participation before day 7, the patient will be replaced and its data excluded from all analyses.

Both intention-to-treat (ITT) and per protocol (PP) analysis will be carried out to study the differences in all outcome measures between the intervention and control group and will be presented. Intention to treat is our primary choice of analysis. The ITT analysis set consists of all randomized patients who did not withdraw before day 7, classified according to allocated treatment regardless of whether they received the assigned treatment and or any protocol deviations. Patients with major protocol deviations will be excluded from the PP analysis set. For patients assigned to the treatment arm, receiving less than 4 out of 8 darbepoetin injections is considered a major protocol violation. Furthermore, in the PP analysis patients will be classified according to treatment assignment.

If the difference between the ITT and PP analysis set is <10%, no per protocol analysis will be performed.

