# 5.8 Replacement of individual subjects after withdrawal

When parents or caregivers want to withdraw their infant for any reason, another infant will be included in the study.

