## 2. Background

The mainstay of antenatal treatment of fetal anemia due to red cell alloimmunization is (serial) IUT. The mainstay of postnatal treatment in HDFN is (1) intensive phototherapy and, if necessary, exchange transfusion to treat hyperbilirubinemia and prevent kernicterus, and (2) postnatal transfusions to treat anemia. Up to 80% of infants with HDFN treated with IUT require at least one postnatal transfusion for anemia during the first 3 months of life, with a median of two postnatal transfusions involving two hospital admissions per infant. Postnatal anemia can be divided in early (up to 7 days of life) due to ongoing hemolysis and late anemia (7 days - 3 months of age).

Two mechanisms are attributed late anemia: “hypo-regenerative anemia” characterized by depressed erythropoiesis and “late anemia of hemolytic disease” caused by persisting antibodies, destroying young erythrocytes. “Hypo-regenerative anemia” occurs in particular in neonates treated with several IUTs as a result of bone marrow suppression. Other contributing factors for late anemia have been reported such as severity of HDFN, reduced use of exchange transfusions during the neonatal period and reduced survival of transfused red blood cells. Finally, erythropoietin deficiency is also considered as a possible contributing factor to late anemia.

Erythropoietin (EPO) has been increasingly used in full-term and particular in preterm neonates to prevent or reduce neonatal anemia without short or long-term adverse effects. Several small studies and casuistic reports suggest that neonates with HDFN may benefit from treatment with EPO to reduce the risk of delayed anemia and subsequent transfusions. However, other authors found that EPO may be less effective than expected. Due to the lack of evidence, routine use of EPO is currently not recommended. To determine a role for EPO in this group of patients, a well-designed randomized controlled clinical trial of sufficient sample size is required. Potentially, EPO stabilizes the hemoglobin levels of these infants and thus prevents anemia, hospital admissions for

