#### 4.2 Study design

Randomized controlled trial without placebo. Included neonates will be randomized at birth to treatment with EPO (intervention group) or “standard care”, with 1:1 allocation, to be randomized in varying blocks of 4 and 6, no stratification is applied. In the treatment group, EPO (darbepoetin alfa) is administered subcutaneously at a dosage of 10  $\mu\text{g}/\text{kg}$  once a week, starting at approximately day 7, for a period of 8 weeks. Treatment is administered during weekly home visits in the treatment arm after discharge from the LUMC. Concomitant therapy with folate (0.25 mg/day) is given in both groups (standard practice). Concomitant iron therapy is given if ferritin level drops below 75 microg/l (standard practice). Weekly routine measurements of complete blood counts (including hemoglobin level, hematocrit and reticulocyte count) will be performed in both groups (standard practice). EPO is discontinued if hemoglobin level is  $\geq$  13 g/dL after at least 4 weeks of treatment with EPO. In EPO treated infants, blood pressure will be measured for safety reasons at onset of treatment, after four weeks and eight weeks. Monthly measurements of liver enzymes (aspartate aminotransferase (ASAT), alanine aminotransferase (ALAT), gamma-glutamyl transferase ( $\gamma$ GT) and lactate dehydrogenase (LDH)) will also be performed in all groups (standard practice). In addition, the neonatal EPO-level will be determined at birth in both groups. The number of postnatal transfusions received during the first 3 months of life and hemoglobin levels prior to the postnatal transfusion are recorded. After initial discharge from the LUMC, postnatal transfusions are recommended to be performed when hemoglobin levels fall below aforementioned cut-off values of hemoglobin.

Because of these clearly defined guideline and hemoglobin measures, blinding of caregivers to treatment allocation and use of a placebo was not deemed necessary.

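### The set that SAP 5.1 calls intention-to-treat leaves out and replaces infants withdrawn before day 7, and no analysis of all randomized infants is planned

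*SAP*

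**What the plan says.** SAP 5.1 (Analysis sets) deals with infants whose parents or caregivers withdraw them from participation after randomization and before day 7. For such an infant, "the patient will be replaced and its data excluded from all analyses". The section then defines the primary set: "The ITT analysis set consists of all randomized patients who did not withdraw before day 7", classified by allocated arm whether or not treatment was given. Infants who stay in the study without injections are therefore kept. The rule concerns only those withdrawn from participation before day 7.

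The Protocol is less specific. Section 5.10 states "Intention to treat analysis is our primary choice of analysis" without defining the set and mentions no day-7 exclusion. Section 5.8 states "When parents or caregivers want to withdraw their infant for any reason, another infant will be included in the study", with no time limit and no statement that the withdrawn infant's data are dropped.

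Two further points matter. SAP 4.3 defines the primary endpoint as "Number of postnatal transfusions per infant from birth up to 3 months of life". SAP 4.2 has infants randomized at birth and EPO started at about day 7, and says "blinding of caregivers to treatment allocation and use of a placebo was not deemed necessary".

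**The concern.** Withdrawal before day 7 happens after randomization. Parents know the arm, so withdrawal may depend on it, for example through disappointment with standard care or reluctance about weekly injections. It may also depend on how ill the infant is in the first days. Removing these infants can make the arms differ in ways that randomization would have prevented.

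Excluding infants who leave before treatment starts is easier to defend when allocation is masked and the endpoint starts with treatment. Neither holds here. The SAP expects primary-endpoint events in the excluded window. Its Background says "Postnatal anemia can be divided in early (up to 7 days of life) due to ongoing hemolysis and late anemia", SAP 4.1 gives a haemoglobin threshold for transfusion on days 0-6, and SAP 5.2 plans to look at transfusions before day 7. The rule can therefore delete outcome data already observed. The result would still be reported as ITT, and readers would not see the comparison of all randomized infants.

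**Working it through.** **1. Does any planned analysis keep these infants?**

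| Analysis | Effect on infants withdrawn before day 7 |
|---|---|
| Primary set (SAP 5.1) | Excluded by definition |
| Per-protocol set (SAP 5.1) | Removes further infants, restores none, and may be skipped |
| Sensitivity analysis with and without transfusions before day 7 (SAP 5.2) | Drops or keeps transfusions, not infants |
| Endpoint from day 7 onward (SAP 4.3) | Same infants as the primary set |

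None does, and the exclusion covers all analyses.

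**2. The plan's own power figure (SAP 4.4).** Inputs: 21 per arm, means 1.9 and 0.8, SDs 1.5 and 0.9, two-sided alpha 0.05.
- Pooled SD = √[(1.5² + 0.9²)/2] = √1.53 = 1.237.
- Standardized difference = 1.1 / (1.237 × √(2/21)) = 2.88.
- Normal approximation: Φ(2.88 − 1.96) = 82.2%. The noncentral t gives 80.3%.

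The stated 81% is reproduced to within 2 points. The drop-out step is 42/0.95 = 44.2, stated as 44. The exact Mann-Whitney power cannot be checked, because the hypothesized distribution is in a figure not available here.

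**3. False-positive rate under informative withdrawal (illustration).** Assumptions not in the documents:
- Counts are negative binomial with mean 1.9 and SD 1.5 in both arms, so the size parameter is 1.9²/(1.5² − 1.9) = 3.61/0.35 = 10.3.
- 22 infants are analysed per arm. The replacement joins the same arm (SAP 5.1 does not say which arm) and is drawn from the same distribution.
- The count before day 7 is a binomial thinning of the total, with 10, 20, 30 or 50% of transfusions falling before day 7. The documents give no share.
- The test is the two-sided Mann-Whitney, tie-corrected with continuity correction, with 400,000 runs per scenario.

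With no selection the rate is 4.8%.

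| Infant(s) replaced | 10% | 20% | 30% | 50% | Shift in mean difference (EPO minus control) |
|---|---|---|---|---|---|
| One EPO infant, lowest early count | 4.8% | 4.9% | 4.9% | 5.1% | +0.01 to +0.05 |
| One EPO infant, highest early count | 5.1% | 5.2% | 5.4% | 5.6% | −0.06 to −0.12 |
| EPO highest plus control lowest | 5.1% | 5.4% | 5.7% | 6.5% | −0.07 to −0.17 |
| Two EPO infants, both highest | 5.5% | 5.8% | 6.2% | 7.0% | −0.10 to −0.20 |

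Selection in the control arm gives the mirror image. Plausibility check: replacing one infant with total m shifts the arm mean by (1.9 − m)/22, so a shift of −0.12 means m is about 1.9 + 22 × 0.12 = 4.5 transfusions.

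Selecting on the full 90-day count would give 6.1% for one EPO infant (highest count) and 8.5% for one infant per arm. This bound cannot be reached, because that count is unknown at day 7.

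**4. What keeping untreated infants costs in power.** EPO counts have mean 0.8 and SD 0.9, and withdrawn EPO infants follow the control distribution.

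| Scenario | Power |
|---|---|
| 21 per arm, none untreated | 77.8% |
| 22 per arm, none untreated | 79.8% |
| 22 per arm, 1 or 2 EPO infants untreated | 75.6% or 70.9% |
| 1 or 2 originals kept, treated replacements added | 76.9% or 73.6% |

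The losses from 79.8% are 4.2 and 8.9 points, or 2.9 and 6.1 points when replacements are added. Only the differences should be used, since the assumed distribution gives 77.8% at 21 per arm against the stated 81%.

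**5. Width of an imputation bound.** Under the assumed distribution the highest count in the trial averages 5.3. Setting one EPO infant to 0 or to that value, with 23 in the arm, moves the arm mean by 5.3/23 = 0.23.

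**The case against.** The strongest reply is that the effect is close to nil. The table above assumes that the infant with the most extreme early count is certain to be the one withdrawn. If each early transfusion instead doubles the odds of being that infant, the rate is 4.8, 4.9 and 5.0% at early shares of 10, 30 and 50%; if it triples them, 4.8, 4.9 and 5.2%. This stands as a point about size.

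The window may also be short. Protocol 5.6 puts consent before randomization and allows it until the end of the first week, so infants consented after birth may be randomized close to day 7. EPO starts at about day 7, so drug effects cannot drive these withdrawals. Both points stand and reduce the likely bias, but an infant consented antenatally can be at risk for the whole week.

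The rule is prespecified, the same in both arms and written out in the definition, and there is a secondary endpoint from day 7 onward. Prespecification does not make withdrawal independent of arm, and that endpoint omits the same infants.

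On feasibility, SAP 4.2 says data were collected with written consent, and the documents do not show that data may be kept after withdrawal. Most of the 90 days would be unobserved, and the 0.23 range from imputation exceeds the 0.06-0.12 shift it guards against. This stands as a limit on the remedy. It is a reason to make the analysis conditional on consent and to treat imputation as a bound, not as the main estimate.

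Finally, on deletion of data the SAP fills a gap left by the Protocol and does not contradict it. That is fair, but it still narrows ITT without changing the label.

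**Conclusion.** The concern holds. SAP 5.1 states an exclusion after randomization, replaces the excluded infants, labels the remainder ITT and makes it primary, and nothing else in the plan recovers the all-randomized comparison. This follows from the text and needs no assumption.

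The effect on the result is conditional. It is nil if no infant is withdrawn before day 7, small for one, and grows with the number. The direction is unknown. The 5% drop-out in SAP 4.4 is an expectation for the whole study and does not cap early withdrawals. All the simulated rates rest on an assumed count distribution, an assumed early share and assumed selection. The case for change rests on the mislabelled primary set and the missing comparison, not on a large inflation of error. It should be fixed, and it does not undermine the design.

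**What to change.** Preferred: define the ITT set as all randomized infants by allocated arm. Keep data already collected and routine transfusion records as far as consent permits, and add replacements to the original infants instead of substituting for them.

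At minimum:
- Rename the current set modified ITT.
- Add a sensitivity analysis of all randomized infants, using the data available under consent. For those without a full count, state two values: the count already observed (0 if none may be used) and the highest count observed in the trial. Assign them in opposite directions in the two arms, then reverse them.
- Report withdrawals before day 7 by arm, with reasons, in the flowchart already listed in SAP 5.1 (Figures and tables).
- Align SAP 5.1 with Protocol 5.8 and 5.10, so that the replacement rule, the handling of data and the meaning of ITT agree.

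The cost is wording and one extra analysis. SAP 4.2 places SAP finalization before database lock and unblinding, so the change can still be prespecified. For some infants, consent may leave only the arm, the reason and the imputed-count analysis. The preferred version dilutes the treatment effect by the power losses worked out above, which assume that full 90-day counts are available for the withdrawn infants.
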